6.11.1. Prohibited Medications and Non-Drug Therapies

The following concomitant medications or therapies are not permitted at any time during the study:

- HIV immunotherapeutic vaccines are not permitted at any time during the study.
- Other experimental agents, antiretroviral drugs not otherwise specified in the protocol, cytotoxic chemotherapy, or radiation therapy may not be administered (see Section 5.2).
- Systemically administered immunomodulators (such as interleukin and interferon agents) are prohibited (a list of examples is provided in the SPM). This includes topical agents with substantial systemic exposure and systemic effects. Use of topical imiquimod is permitted.
- Acetaminophen (paracetamol) cannot be used in participants with acute viral hepatitis [James, 2009].
- Chronic use of systemic (oral or parenteral) glucocorticoids must be avoided due to the immunosuppressive effect and potential decreases in RPV plasma

concentrations; however, short treatment courses with oral prednisone/prednisolone/methylprednisolone (e.g. adjunctive treatment of pneumocystis pneumonia with 21 days of tapering prednisone) are allowed. A single dose of systemic dexamethasone is permitted, but more than a single dose in a treatment course may cause a significant decrease in RPV plasma concentration and is prohibited. Topical, inhaled or intranasal use of glucocorticoids will be allowed.

Note: Any prohibited medications that decrease CAB or RPV concentrations should be discontinued for a minimum of four weeks or a minimum of three half-lives (whichever is longer) prior to the first dose and any other prohibited medications should be discontinued for a minimum of two weeks or a minimum of three half-lives (whichever is longer) prior to the first dose.

For additional information on concurrent therapies and interactions suspected to be relevant to other antiretroviral therapy used during the study (e.g. BIK), please consult the current BIC Investigator brochure and local prescribing information.

Concurrent with CAB and/or RPV

For participants receiving **either formulation** of CAB and/or RPV, the following medications could significantly decrease the levels of CAB and/or RPV due to enzyme induction and therefore must not be administered concurrently:

- Carbamazepine
- Oxcarbazepine
- Phenobarbital
- Phenytoin
- Rifabutin
- Rifampicin / Rifampin
- Rifapentine
- St. John's wort (*Hypericum perforatum*)

Concurrent with RPV

In addition, participants must discontinue the following (or change to an allowable alternative) while receiving treatment with RPV:

- Oral RPV: proton pump inhibitors, such as esomeprazole, lansoprazole, omeprazole, pantoprazole, rabeprazole;
- Both Oral and RPV LA: systemic dexamethasone (more than a single dose).

If the participant cannot discontinue use or change to an allowable alternative while receiving treatment with RPV, the participant should not be randomized into the study.

Please refer to the current RPV Investigator brochure and local prescribing information for other drugs that are prohibited, should be used with caution, require dose adjustment, or increased clinical monitoring if taken with oral RPV.

Concurrent with either CAB LA or RPV LA

In addition, for participants receiving CAB LA and RPV LA, use of anticoagulation agents for greater than 14 days is prohibited, with the exception of the use of anticoagulation for DVT prophylaxis (e.g., postoperative DVT prophylaxis) or the use of low dose aspirin (daily doses ≤ 325 mg). Systemic anticoagulation (including prophylaxis doses) on the day of an IM injection should be avoided.

Concurrent with BIK

The following medications or their equivalents may cause decreased concentrations of BIC. Therefore, the following medications must not be administered concurrently with BIC:

- Carbamazepine
- Oxcarbazepine
- Phenobarbital
- Phenytoin
- Rifampicin / Rifampin
- Rifabutin
- Rifapentine
- St. John's wort (*Hypericum perforatum*)

- Dofetilide is prohibited as BIC may inhibit renal tubular secretion resulting in increased dofetilide/pilsicainide concentrations and potential for toxicity.

Note: Any prohibited medication that decrease BIC concentrations should be discontinued for a minimum of four weeks or a minimum of three half-lives (whichever is longer) prior to the first dose. Any other prohibited medication should be discontinued for a minimum of two weeks or a minimum of three half-lives (whichever is longer) prior to the first dose.

Please refer to the current local prescribing information for other drugs that should be used with caution, require dose adjustment, or increased clinical monitoring if taken with BIK.

6.12. Dose Modification

No dose reductions, modifications, or changes in the frequency of any components of each regimen will be allowed during the study beyond what is allowed within the protocol or directly approved by the study Medical Monitor. Protocol waivers or

exemptions are not allowed. Therefore, adherence to the study design requirements is essential and required for study conduct.

In exceptional circumstances, and in consultation with the Medical Monitor, Investigators may provide oral CAB and/or RPV as a short-term “bridging” strategy for participants who have begun CAB LA + RPV LA (see Section 6.8.1 for additional details). Should a participant need “oral bridging”, sites must contact the Medical Monitor for guidance on treatment strategies prior to a missed CAB LA + RPV LA dose. Should a participant not notify the site in advance, the Medical Monitor must be contacted for further treatment guidance.

Please refer to [Appendix 11](#) in Section 10.11 for study management information during the COVID-19 pandemic.

Supplementary study conduct information not mandated to be present in this protocol is provided in the accompanying Study Procedures Manual (SPM), which is available on the online Study Web Portal. The SPM will provide the site personnel with administrative and detailed technical information.

7. DISCONTINUATION OF STUDY INTERVENTION AND PARTICIPANT DISCONTINUATION/WITHDRAWAL

7.1. Participant Discontinuation/Withdrawal from the Study

Participants permanently discontinuing study treatments prior to the Month 12 visit are considered to be withdrawn from the study treatments. Participants who enter the Extension Phase but permanently discontinue participation in the Extension Phase prior to commercially available CAB LA + RPV LA are considered to be withdrawn from the study treatments but are not considered to be withdrawn from the study because they will enter the follow Follow-up Phase.

A participant may withdraw consent and discontinue participation in this study at any time at his/her own request. The investigator may also, at his or her discretion, discontinue the participant from participating in this study at any time (e.g., safety, behavioral or administrative reasons). Participants may have a temporary interruption to their study treatment for management of toxicities. If a participant withdraws from the study, he/she may request destruction of any samples taken, and the investigator must document this in the site study records. Withdrawn participants will not be replaced.

All participants who discontinue prematurely from the study, irrespective of arm, will be asked for additional information to establish the reason for withdrawal.

Participants are not obligated to state the reason for withdrawal. However, the reasons for withdrawal, or failure to provide a reason, must be documented by the Investigator on the Completion/Withdrawal Section of the electronic case report form (eCRF). Every effort should be made by the Investigator to follow-up participants who withdraw from the study.

An in-clinic withdrawal visit will also be used to assess participants with ongoing AEs, and serious adverse events (SAEs) related & not related to study drug and also any laboratory abnormalities that are considered to be AEs or potentially harmful to the participant. The withdrawal visit will be distinct from visits conducted during the LTFU Phase.

Following completion of withdrawal assessments, all participants who received one or more injections of CAB LA+ RPV LA will subsequently enter the LTFU Phase initiating with the Month 3 LTFU visit.

Withdrawal decision coincides with a planned clinic visit:

- For any participant who withdraws prematurely from the Maintenance or Extension Phase during a planned in-clinic study visit, withdrawal assessments and procedures are to be performed (according to the SoA (Section 1.3) instead of the assessments for the active planned visit during which the withdrawal decision is made.

Withdrawal decision occurs between planned clinic visits:

- In the event that a decision to withdraw a participant occurs between clinic visits, participants will be instructed to return for an unscheduled withdrawal visit (within 8 weeks of the last Q2M LA injection received or within 4 weeks if participant is randomised to BIK or during the administration of the OLI (oral CAB and oral RPV) if randomized to CAB LA + RPV LA and choosing to perform the OLI) during which withdrawal assessments according to the SoA (Section 1.3) will be completed. For participants who received one or more injections of CAB LA+ RPV LA **withdrawal assessments must occur prior to initiation of the next ART regimen.**

If withdrawal coincides with the active planned Month 13 visit, HIV-1 RNA will only be assessed if the last HIV-RNA measurement from Month 12 was ≥ 50 copies per mL (i.e. retest for viral load blip). This will ensure that only the Month 12 viral load assessment or required retest will be counted towards the primary and secondary efficacy endpoint windows.

The in-clinic visit will be recorded as an unscheduled withdrawal visit with the following exception. A withdrawal visit and assessments coinciding with the planned Month 13 visit will be recorded as the Month 13 visit such that the participant can be considered a completer, consistent with the definition of study completer in Section 4.5.

Participants may be prematurely discontinued from the study treatment for any of the following reasons:

- Adverse event / Serious adverse event
- Protocol deviation
- Intolerability of injections
- Participant lost to follow-up
- Participant or Investigator non-compliance;
- Termination of the study by the Sponsor
- At the request of the participant, Investigator, GSK or ViiV Healthcare;
- The participant requires concurrent prohibited medications during the course of the study. The participant may remain in the study if in the opinion of the Investigator and the medical monitor; such medication will not interfere with the conduct or interpretation of the study or compromise the safety of the participant.

Participants must be discontinued from study treatment for any of the following reasons:

- Participants who are not eligible to continue into the Maintenance Phase.
- Participants who are not eligible, or do not wish to continue on to the Extension Phase.
- Virologic withdrawal criteria as specified in Section 7.1.6 are met;
- Participant requires substitution of ART;
- Participant requires substitution or dose reduction of CAB LA or RPV LA (oral bridging supply and potential for a second loading dose may be permissible following discussion with the Medical Monitor).
- Liver toxicity where stopping criteria are met and no compelling alternate cause is identified (see Section 7.1.2);
- Renal toxicity is met and no compelling alternate cause is identified;
- QT interval (QTc) interval >550 msec from three or more tracings separated by at least 5 minutes and considered causally related to IP.
- Grade 4 clinical AE considered causally related to study drug;
- Participant has a Grade 3 or higher rash or Grade 2 rash with evidence of systemic involvement and no compelling alternative cause is identified
- Pregnancy (intrauterine), regardless of termination status of pregnancy (for participants on BIK only) Participant withdrew consent

Efficacy data for participants withdrawing from the study will be considered evaluable up to the point at which they are withdrawn using the same criteria for evaluability as for participants who complete the study.

Safety data for all participants who receive any amount of study drug, including participants who withdraw from the study, will be included in evaluations of safety.

All data from the Withdrawal visit will be recorded, as they comprise an essential evaluation that should be done prior to discharging any participant from the study.

The following actions must be taken in relation to a participant who fails to attend the clinic for a required study visit:

- a. The site must attempt to contact the participant and re-schedule the missed visit as soon as possible.
- b. The site must counsel the participant on the importance of maintaining the assigned visit schedule and ascertain whether or not the participant wishes to and/or should continue in the study.
- c. In cases where the participant is deemed 'lost to follow up', the investigator or designee must make every effort to regain contact with the participant (where possible, 3 telephone calls and if necessary, a certified letter to the participant's

last known mailing address or local equivalent methods). These contact attempts should be documented in the participant's medical record.

- d. Should the participant continue to be unreachable, only then will he/she be considered to have withdrawn from the study with a primary reason of "Lost to Follow-up".

A participant may withdraw from study treatment at any time at his/her own request or may be withdrawn at any time at the discretion of the investigator for safety, behavioral or administrative reasons. If a participant withdraws from the study, he/she may request destruction of any samples taken, and the investigator must document this in the site study records.

7.1.1. Liver monitoring event – Increased monitoring

A liver monitoring event is an occurrence of predefined liver chemistry changes that triggers increased monitoring of the participant's liver chemistries, but no action is taken with study treatment unless liver chemistry stopping criteria are met.

Liver monitoring event criteria:

- Baseline ALT $\leq 1.5x$ ULN: ALT $\geq 5x$ ULN and $< 8x$ ULN and bilirubin $< 2x$ ULN without symptoms believed to be related to liver injury or hypersensitivity.
- Baseline ALT $> 1.5x$ ULN: ALT $\geq 3x$ baseline and $< 5x$ baseline and bilirubin $< 2x$ ULN without symptoms believed to be related to liver injury or hypersensitivity

Actions:

- Notify the VH medical monitor within 24 hours of learning of the abnormality to discuss participant safety.
- Participant can continue study intervention
- Participant must return every 2 weeks for repeat liver chemistries (ALT, AST, alkaline phosphatase, bilirubin) until resolution or stabilisation (ALT $< 5 \times$ ULN on 2 consecutive evaluations)
- If at any time participant meets the liver chemistry stopping criteria, proceed as described below

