8.3.4. Prompt Reporting of Serious Adverse Events and Other Events

SAEs, pregnancies, and liver function abnormalities meeting pre-defined criteria will be reported promptly by the investigator to the medical monitor once the investigator determines that the event meets the protocol definition for that event. Any seizure or suspected seizure should be reported in an expedited manner, as noted in Table 5.

Criteria for liver chemistry stopping and follow-up criteria are in Section 7.1.1.

Table 5 Reporting of Serious Adverse Events and Other Events

Type of Event	Initial Reports		Follow-up Information on a Previous Report	
	Time Frame	Documents	Time Frame	Documents
All SAEs	24 hours	“SAE” data collection tool	24 hours	Updated “SAE” data collection tool
Cardiovascular or death event	Initial and follow-up reports to be completed when the cardiovascular event or death is reported ^a	“CV events” and/or “death” data collection tool(s) if applicable	Initial and follow-up reports to be completed when the cardiovascular event or death is reported ^a	Updated “CV events” and/or “death” data collection tool(s) if applicable
Pregnancy	24 hours	“Pregnancy Notification Form”	Within 24 hours of investigator awareness of pregnancy outcome	“Pregnancy Follow-up Form” and SAE if required
Seizure or suspected seizure	24 hours	eCRF	24 hours	eCRF
Suspected ABC HSR in participants receiving Oral SOC during the Long-Term Follow-Up Phase ^b	1 week	ABC HSR eCRF	1 week	Updated ABC HSR eCRF
ALT $\geq 3 \times$ ULN and bilirubin $\geq 2 \times$ ULN (>35% direct) (or ALT $\geq 3 \times$ ULN)	24 hours ^c	“SAE” data collection tool. “Liver Event eCRF” and “Liver Imaging” and/or “Liver Biopsy” eCRFs, if applicable ^d	24 hours	Updated “SAE” data collection tool/“Liver Event” documents ^d
ALT $\geq 5 \times$ ULN that persists ≥ 2 weeks	24 hours ^c	Liver Event eCRF ^d	24 hours	Updated Liver Event eCRF ^d
ALT $\geq 8 \times$ ULN	24 hours ^c	Liver Event eCRF ^d	24 hours	Updated Liver Event eCRF ^d
ALT $\geq 3 \times$ ULN (if baseline ALT is <ULN) or ALT ≥ 3 fold increase from baseline value with appearance or worsening of symptoms of hepatitis or hypersensitivity	24 hours ^c	Liver Event eCRF ^d	24 hours	Updated Liver Event eCRF ^d

- Additional details and time frames for reporting supplementary information for cardiovascular and death events are provided in Section 8.3.9.
- ABC HSR eCRF only required if event meets one of the ICH E2A definitions of seriousness.

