8.3.10.3. Grade 3 Toxicity/Adverse Event

Participants who develop a Grade 3 AE or toxicity should be managed as follows:

- If the Investigator has compelling evidence that the Grade 3 AE or toxicity has not been caused by IP, dosing may continue after discussion with the Medical Monitor.
- Participants who develop a Grade 3 AE or toxicity, which the Investigator considers related or possibly related to the IP, should have the IP withheld and be rechecked each week until the AE returns to Grade 2. Once the AE is Grade ≤ 2 , IP may be re-started.
- Should the same Grade 3 AE recur within 28 days in the same participant, the IP should be permanently discontinued and the participant withdrawn from study.
- Participants experiencing Grade 3 AEs requiring permanent discontinuation of IP should be followed weekly until resolution of the AE and to have withdrawal study evaluations completed. A follow-up visit should be performed 4 weeks after the last dose of IP. Any participant receiving at least one dose of CAB LA and /or RPV LA who discontinue IP / Withdraw will initiate treatment with HAART and enter the LTFU Phase for 52 weeks of follow up.
- Participants with Grade 3 asymptomatic laboratory abnormalities should be investigated for all potential non-drug related causes, and, following discussion with the Medical Monitor, may continue IP if the Investigator has compelling evidence that the toxicity is not related to IP, with the exception of liver chemistry stopping criteria (See Section 8.3.11.1). Isolated Grade 3 lipid abnormalities do not require withdrawal of IP.

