8.3.10.4. Grade 4 Toxicity/Adverse Event

- Participants who develop a Grade 4 AE or toxicity must have IP permanently discontinued. However, if the Investigator has compelling evidence that the AE is not causally related to the IP, dosing may continue after discussion with, and assent from, the Medical Monitor. Participants should be rechecked each week until the AE returns to Grade 2.
- Participants experiencing Grade 4 AEs requiring permanent discontinuation of IP should be followed weekly until resolution of the AE and encouraged to complete the withdrawal and follow-up study evaluations as noted above. Any participant receiving at least one dose of CAB LA and /or RPV LA who discontinue IP / Withdraw will initiate treatment with HAART and enter the LTFU Phase for 52 weeks of follow up.
- Participants with Grade 4 asymptomatic laboratory abnormalities should be investigated for all potential non-drug related causes, and, following discussion with the Medical Monitor, may continue therapy if the Investigator has compelling evidence that the toxicity is not related to IP, with the exception of liver chemistry stopping criteria (See Section 8.3.11.1). An in-clinic follow-up visit will be performed approximately 4 weeks after the last dose of study medication if AEs, SAEs, or laboratory abnormalities considered potentially harmful to the participant are ongoing at the last on-study visit. Isolated Grade 4 lipid abnormalities do not require withdrawal of IP.

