8.3.11.1. Liver Chemistry Stopping and Follow-up Criteria

Liver chemistry threshold stopping criteria have been designed to assure participant safety and to evaluate liver event etiology during administration of study drug and the follow-up phase.

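### For asymptomatic, possibly related ALT in the Section 7.1.1 monitoring band, 7.1.1 leaves dosing unchanged while 8.3.10.3 withholds it, with no stated precedence; repeat testing is two-weekly in 7.1.1 but weekly in 7.1.2.1

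*Protocol*

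**What the plan says.** **Liver rule (Protocol 7.1.1).** The monitoring event is ALT of 5 to <8xULN when baseline ALT is at most 1.5xULN, or 3 to <5 times baseline when baseline is higher. Bilirubin must be below 2xULN and there must be no related symptoms. In this band "no action is taken with study treatment unless liver chemistry stopping criteria are met", and the listed actions include "Participant can continue study intervention". The Medical Monitor is notified within 24 hours and chemistries are repeated every 2 weeks. Relatedness is not mentioned.

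**Grade rule (Protocol 8.3.10.3).** A participant with a Grade 3 toxicity "which the Investigator considers related or possibly related to the IP, should have the IP withheld and be rechecked each week"; restart is allowed once it is Grade 2 or lower. A separate bullet covers asymptomatic Grade 3 laboratory abnormalities. After discussion with the Medical Monitor, IP may continue if there is compelling evidence of no relation to IP, "with the exception of liver chemistry stopping criteria (See Section 8.3.11.1").

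**Grade 4 rule (Protocol 8.3.10.4).** "Participants who develop a Grade 4 AE or toxicity must have IP permanently discontinued", unless there is compelling evidence of no causal relation.

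**Follow-up (Protocol 7.1.2.1).** Any participant who develops ALT of at least 5xULN must be followed weekly.

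**The concern.** The same ALT result attracts two dosing instructions whenever relatedness is not excluded. Either choice has a cost. Continuing keeps a possibly hepatotoxic drug going. Withholding interrupts suppressive therapy, and Section 6.9 then requires every antiretroviral to be held. A site can be recorded as deviating whichever section it follows.

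The follow-up intervals also differ. Here the shorter interval matters for safety, because a rise to 8xULN or more is an immediate stopping event in Table 3.

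**Working it through.** No figure in the protocol needs reproducing. The check maps the bands to grades and then compares the instructions.

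**1. Grade of the monitoring band.** Appendix 4 grades ALT 2.5 to <5xULN as Grade 2, 5 to <10xULN as Grade 3 and 10xULN or more as Grade 4.

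- Baseline at most 1.5xULN: the band 5 to <8xULN lies wholly inside 5 to <10xULN, so it is all Grade 3.
- Baseline b above 1.5xULN: the band runs from 3b to <5b. The lower end is Grade 3 when 3b is at least 5, so b is at least 1.67. The whole band stays below 10xULN when 5b is at most 10, so b is at most 2.
 - b from 1.67 to 2: all Grade 3.
 - b between 1.5 and 1.67: the lowest part (from about 4.5 to <5xULN) is Grade 2.
 - b above 2: the top can reach Grade 4, unless the 500 U/L stopping limit in Table 3 comes first. The protocol gives no ULN. If it is 40 U/L, 500/40 = 12.5xULN, so a Grade 4 part exists; if it is 50 U/L, 500/50 = 10.0xULN, so none does.

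**2. Instructions for a Grade 3 value in the band.**

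| Relatedness | 7.1.1 | 8.3.10.3 |
|---|---|---|
| Compelling evidence of no relation | May continue | May continue after Medical Monitor discussion |
| Related or possibly related | May continue | Withhold, recheck weekly, restart at Grade 2 or lower |

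The sections part only in the second row.

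**3. Is precedence stated?** Three places point to the liver rules.

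- Section 7.1 lists, among the reasons for mandatory discontinuation, "Liver toxicity where stopping criteria are met and no compelling alternate cause is identified".
- Section 8.3.10.1 introduces the grade rules as general management guidance.
- Table 3 makes ALT of 5 to <8xULN a stopping event once it persists for 2 weeks, which presupposes that dosing may go on meanwhile.

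None of these ranks the two rules. The one liver exception in 8.3.10.3 concerns stopping criteria, not the monitoring band, and it removes permission to continue. It cites 8.3.11.1, which says only that "Liver chemistry threshold stopping criteria have been designed to assure participant safety" and to evaluate the cause of liver events; it contains no criterion or dosing rule. Section 8.3.4 says that "Criteria for liver chemistry stopping and follow-up criteria are in Section 7.1.1", but the stopping criteria are in 7.1.2 and the follow-up in 7.1.2.1.

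**4. Test interval.** In the first 14 days, 7.1.1 gives 14/14 = 1 test and 7.1.2.1 gives 14/7 = 2. A rise to 8xULN or more in the first week would be seen at day 7 on the weekly schedule and at day 14 on the other, 7 days later. The weekly rule is not confined to stopping events: it depends only on ALT of at least 5xULN, and 7.1.2.1 gives stopping events their own twice-weekly schedule.

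**5. Where dosing could differ.** The shortest scheduled injection gap is one month less the 7-day window: 28 - 7 = 21 to 31 - 7 = 24 days. By then a value still in the band has passed the 2-week point and is a stopping event, so scheduled injections are largely unaffected. What remains is mainly daily oral dosing, chiefly BIK (654/3 = 218 planned participants), with scheduled chemistry at Months 2, 4, 6, 8 and 10 while daily doses continue. Section 8.3.10.2 requires consultation at ALT of at least 3xULN, but only for CAB LA + RPV LA.

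**The case against.** The best defence is that a specific liver algorithm beside a general grade rule is ordinary drafting, and the three places in step 3 show which one is meant. The bullet for asymptomatic laboratory abnormalities does not itself order withholding; that order sits in the broader Grade 3 bullet. Section 7.1.1 permits rather than requires continuation. The Medical Monitor hears of every case within 24 hours in both arms, Section 6.9 routes interruption decisions through the Medical Monitor, and investigators may interrupt at their discretion. BIK participants have at least 6 months of prior exposure (inclusion criterion 5).

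Most of this stands, and it limits the weight of the point. It does not supply the missing sentence: the Medical Monitor is told to discuss the case but not which rule applies. It also leaves the interval mismatch untouched.

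Three stronger readings are tempting and are not supported:

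- **That sites face two irreconcilable orders with material harm.** The text leans to the liver rules and the Medical Monitor mediates. Counting BIK doses taken under one rule and not the other would measure the instructions, not patient impact.
- **That the two test intervals cannot both be met.** Weekly testing satisfies both, and Table 3 accepts monitoring every 1 to 2 weeks. The breach arises only for a site that follows 7.1.1 alone.
- **That the liver rules should override all grade rules.** Placing them above 8.3.10.4 would let possibly related Grade 4 ALT continue when baseline exceeds 2xULN.

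**Conclusion.** The point holds in limited form. For asymptomatic, related or possibly related ALT in the monitoring band, 7.1.1 and 8.3.10.3 give different dosing instructions and nothing ranks them, although the wording favours 7.1.1 and 7.1.2. The overlap is the whole band when baseline ALT is at most 1.5xULN and can be partial at higher baselines; the extent of any Grade 4 part depends on a ULN that the protocol does not state. The interval mismatch is a separate defect, worth one test in the first two weeks and up to a week's delay in detecting a stopping event.

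Practical risk is limited and falls mainly on BIK and on unscheduled tests. No count of affected participants and no effect on any endpoint or analysis is claimed. The correction should be made because it is specific, cheap and bears on safety.

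**What to change.** 1. In 7.1.1, set the repeat interval to weekly when ALT is at least 5xULN, to match 7.1.2.1.
2. In 8.3.10.3, add one sentence: Grade 3 ALT that falls in the monitoring band is managed under 7.1.1 and 7.1.2, with Medical Monitor discussion before dosing continues in either arm, including BIK. Leave 8.3.10.4 in force for any ALT of 10xULN or more.
3. As editorial corrections, point 8.3.4 and the exceptions in 8.3.10.3 and 8.3.10.4 to 7.1.2.

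The cost is one sentence, one interval and three pointers in the next amendment, with a site memo. Sites that had followed 7.1.1 alone would draw one more sample in the first two weeks after a qualifying result. The stopping thresholds do not change.
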